2. STUDY OBJECTIVES AND ENDPOINTS

2.1. Objectives

Primary objective: Test for the non-inferiority of sildenafil 80 mg vs. 5 mg for mortality; mortality rate with the 80 mg dose is no worse than double the mortality rate for the 5 mg dose.

2.2. Endpoints

This study will use an independent endpoint adjudication committee to determine whether certain investigator-reported events meet the definition of disease-related efficacy endpoints, using pre-defined endpoint criteria.

For those serious adverse events (SAEs) that are handled as disease related efficacy endpoints (which may include death), a data monitoring committee (DMC) will conduct unblinded reviews on a regular basis throughout the trial (see Data Monitoring Committee Section).

Any SAE that is adjudicated by the endpoint adjudication committee NOT to meet endpoint criteria is reported back to the investigator site of incidence; the investigator at the study site must evaluate and report that SAE to Pfizer, in accordance with the time frames described in the Serious Adverse Event Reporting Requirements section of this protocol. The investigator's SAE awareness date in this instance is identified as the date on which the investigator site of incidence receives the nonendpoint SAE back from the endpoint adjudication committee. Handling these SAEs in this manner will allow Pfizer to meet its sponsor reporting obligations to regulatory authorities upon receipt of such SAEs.

However, when the investigator has judged the SAE to have a causal relationship with the investigational product, the investigator must additionally report the event to the sponsor as described in the Serious Adverse Event Reporting Requirements section, even if that event is a component of the endpoint.

Any events that remain unadjudicated at the annual safety report cutoff date will not be included in the safety tables of the report.

Primary Efficacy Endpoint:

- Time to death (Mortality).

Secondary Efficacy Endpoints:

- Time to first event (Clinical Worsening); and
- 6MWD at Months 6 and 12.

Clinical worsening⁸ for the purpose of this study is defined as:

- All-cause mortality;
- Hospital stay for worsening PAH (including but not limited to right heart failure [RHF], initiation of prostanoids, lung transplantation, or septostomy); or

- Disease progression (defined as a reduction from baseline in the 6MWD test by at least 15% and worsening functional class from baseline, both confirmed by a 2nd test/evaluation within 2 weeks (cannot be performed on same day). Patients with functional class IV at baseline only need to meet the 6MWD criteria as they cannot have deterioration in functional class. The date of the event will be the first date of the two 6MWTs.

3. STUDY DESIGN

This is a randomized, double-blind, parallel-group study in adult subjects with PAH that is designed to assess mortality during long-term treatment with sildenafil at three doses. Four hundred and twenty-nine (429) subjects will be enrolled to allow approximately 143 subjects to be randomly assigned to each arm. Approximately 80-120 sites with experience conducting PAH trials will participate in the study. The study is expected to complete enrollment in approximately 4.3 years with total duration of about 7.7 years to reach required number of events (143 deaths).

Subjects will be randomly assigned on a 1:1:1 basis to either blinded sildenafil 5 mg (TID), 20 mg (TID) or 80 mg (TID) at the Baseline visit (Day 1) after successfully fulfilling all inclusion and exclusion criteria. Randomization will be stratified according to PAH treatment at entry (PAH-treatment naïve vs. on PAH-treatment) and etiology of PAH (idiopathic vs. secondary to CTD/surgical repair). Blinded sildenafil treatment is to continue for the duration of the subject's participation in the study. Subjects who discontinue from the trial will continue to be followed for the primary endpoint.

4. SUBJECT SELECTION

This study can fulfill its objectives only if appropriate subjects are enrolled. The following eligibility criteria are designed to select subjects for whom protocol treatment is considered appropriate. All relevant medical and non-medical conditions should be taken into consideration when deciding whether this protocol is suitable for a particular subject. These criteria must be met before a subject is randomly assigned into the study. Subject eligibility should be reviewed and documented by an appropriately qualified member of the investigator's study team before subjects are included in the study. Current country label or Investigator's Brochure should be consulted to determine other conditions that would exclude subjects from treatment with sildenafil citrate.

4.1. Inclusion Criteria

Subjects must meet all of the following inclusion criteria to be eligible for enrollment into the study:

1. Subjects ≥ 18 and < 75 years of age with any of the following conditions:
 - a. Idiopathic Pulmonary Arterial Hypertension (IPAH); or
 - b. PAH secondary to connective tissue disease (CTD); or

- c. PAH with surgical repair (at least 5 years previously) of atrial septal defect (ASD), ventricular septal defect (VSD), patent ductus arteriosus (PDA) and aorto-pulmonary window.
2. PAH must have been newly diagnosed (confirmed by right heart catheterization) within 12 months prior to randomization (mean pulmonary artery pressure (mPAP) ≥ 25 mmHg at rest, pulmonary capillary wedge pressure (PCWP) or left ventricular end diastolic pressure (LVEDP) ≤ 15 mmHg, and pulmonary vascular resistance (PVR) > 4 mmHg/L/min or $320 \text{ dynes} \cdot \text{sec}/\text{cm}^5$);
3. No prior long term PDE-5 inhibitor treatment (Prior episodic use of PDE-5 inhibitors for erectile dysfunction or prior limited trial use (maximum of 4 weeks) provided that PDE-5 was not discontinued for lack of efficacy or adverse event does not disqualify a subject from the study);
4. PAH WHO Functional Class II-IV;
5. Baseline 6MWD ≥ 50 m.
6. Male or female subjects not of childbearing potential or female subjects of childbearing potential who agree to use a highly effective method of contraception throughout the study **and for at least 28 days after the last dose of assigned treatment**. Female subjects who are not of childbearing potential include those who meet at least one of the following criteria:
 - a. Have undergone a documented hysterectomy and/or bilateral oophorectomy;
 - b. Have medically confirmed ovarian failure or;
 - c. Achieved post-menopausal status, defined as the cessation of regular menses for at least 12 consecutive months with no alternative pathological or physiological cause and a serum FSH level within the laboratory's reference range for postmenopausal females.
7. Willing and able to comply with scheduled visits, treatment plan, laboratory tests, and other trial procedures; and
8. Evidence of a personally signed and dated informed consent document indicating that the subject (or a legal representative) has been informed of all pertinent aspects of the study.

4.2. Exclusion Criteria

Subjects presenting with any of the following will not be included in the study:

1. PAH secondary to any etiology other than those specified in the inclusion criteria;
2. Significant (ie, $> 2+$) valvular disease other than tricuspid regurgitation or pulmonary regurgitation;

3. Congenital heart disease (unless they meet inclusion criteria in [Section 4.1](#)) or pulmonary hypertension due to thromboembolism;
4. Atrial septostomy within 6 months prior to randomization (subjects who are required to undergo this procedure during the study should be withdrawn);
5. Myocardial infarction, unstable angina, cerebrovascular accident (CVA), or transient ischemic attack (TIA) within 6 months prior to randomization;
6. Acutely decompensated heart failure within 3 months prior to randomization;
7. History of cardiac arrest, respiratory arrest, hemodynamic collapse, CPR, ventricular tachycardia, ventricular fibrillation, or uncontrolled atrial fibrillation;
8. History of pulmonary embolism verified by ventilation/perfusion scan, angiogram or spiral chest computerized tomography scan;
9. Hypotension defined as systolic arterial pressure <90 mmHg or diastolic arterial pressure <50 mmHg after sitting for 5 minutes at either Screening or Day 1;
10. Previous long term treatment with PDE-5 inhibitors (Prior episodic use of PDE-5 for erectile dysfunction or prior limited trial use (maximum of 4 weeks) provided that PDE-5 was not discontinued for lack of efficacy or adverse event does not disqualify a subject.);
11. Treatment with bosentan or riociguat within 3 months of randomization;
12. Current treatment with nitrates or nitric oxide;
13. Initiation of new therapy for PAH <3 months prior to randomization or change in background treatment specific for PAH within 30 days prior to randomization (ie, ambrisentan and any other ETRA or novel agent that becomes available during the conduct of the study provided that the new agent is not a potent CYP3A inducer or inhibitor (Appendix 1) that has a clinically evident drug-drug interaction with sildenafil and/or prostanoids);
14. Change in class of supportive therapy used for adjunctive treatment of PAH within 30 days prior to randomization (eg, oxygen, calcium channel blockers, digoxin, diuretics);
15. Current treatment with potent CYP3A4 inhibitors or inducers (Appendix 1);
16. History of chronic obstructive or restrictive lung disease (eg, chronic obstructive pulmonary disease (COPD) or scleroderma) with impairment of lung function demonstrated by total lung capacity (TLC) <70% predicted, or forced expiratory volume (FEV₁) <60% predicted. (Subjects with these pulmonary disorders must have Pulmonary Function Tests performed prior to study entry if they have not been performed in the previous 12 months). If either TLC or FEV₁ do not meet criteria above but in the Investigator's judgment the patient does not have chronic or restrictive lung disease, the Investigator is to contact the sponsor to determine if patient can be enrolled;

17. Within 5 years of Screening, history of malignancy (except for adequately treated basal cell or squamous cell carcinoma of the skin), human immunodeficiency virus (HIV) or any other disease likely to limit life expectancy;
18. Known allergy or adverse reaction to sildenafil or any other ingredient in Revatio®;
19. Known hereditary degenerative retinal disorders, such as retinitis pigmentosa, history of visual loss, untreated proliferative diabetic retinopathy, or history of non-arteritic ischemic optic neuropathy (NAION);
20. Known priapism, hearing loss, vision changes, or epistaxis due to any episodic use of PDE-5 inhibitor;
21. History of alcoholism or drug abuse, or prior symptoms of drug- or alcohol-related withdrawal;
22. Participation in any other experimental studies involving other drug or non-drug therapies within 30 days before the current study begins and during study participation;
23. Pregnant females; breastfeeding females; females of childbearing potential who are unwilling or unable to use a highly effective method of contraception as outlined in this protocol for the duration of the study and for at least 28 days after last dose of investigational product;
24. Any severe acute or chronic medical or psychiatric condition or laboratory abnormality that may increase the risk associated with trial participation or investigational product administration or may interfere with the interpretation of trial results and, in the judgment of the investigator, would make the subject inappropriate for entry into this trial; or
25. Subjects who are investigational site staff members directly involved in the conduct of the trial and their family members, site staff members otherwise supervised by the Investigator, or subjects who are Pfizer employees directly involved in the conduct of the trial.

4.3. Life Style Guidelines

All female subjects who, in the opinion of the investigator, are biologically capable of having children and are sexually active, must agree to use a highly effective method of contraception consistently and correctly for the duration of the active treatment period and for at least 28 days after the last dose of investigational product. The investigator, in consultation with the subject, will select the most appropriate method of contraception for the individual subject from the permitted list of contraception methods, and instruct the subject in its consistent and correct use. The investigator, at each study visit, will confirm and document consistent and correct use. In addition, the investigator will instruct the subject to call immediately if the selected birth control method is discontinued or if pregnancy is known or suspected.

Highly effective methods of contraception are those that, alone or in combination, result in a failure rate of less than 1% per year when used consistently and correctly (ie, perfect use) and include:

1. Established use of oral, inserted, injected or implanted hormonal methods of contraception are allowed provided the subject remains on the same treatment throughout the entire study and has been using that hormonal contraceptive for an adequate period of time to ensure effectiveness.
2. Correctly placed copper containing intrauterine device (IUD);
3. Male condom or female condom used WITH a spermicide (ie, foam, gel, film, cream, suppository);
4. Male sterilization with appropriately confirmed absence of sperm in the post-vasectomy ejaculate; and
5. Bilateral tubal ligation or bilateral salpingectomy.

Alternate language for Sweden (or any other country preference).

To qualify as a highly-effective method for birth control the method must offer a documented protection from pregnancy with a pearl index of <1 (according to the ICH M3 definition). Male condom or female condom used with a spermicide as well as oral low-dose gestagens does not qualify as highly-effective methods for birth control. The following methods for birth control (with typical use) offers a protection from pregnancy with a pearl index of < 1 and can be accepted by MPA as highly effective;

1. Oral (except low-dose gestagen (lynestrenol and norestisteron), injectable, or implanted hormonal contraceptives);
2. Intrauterine device;
3. Intrauterine system (for example, progestin-releasing coil);
4. Vasectomized male (with appropriate postvasectomy documentation of the absence of sperm in the ejaculate);
5. Bilateral tubal occlusion;
6. Abstinence from penile-vaginal intercourse, when this is the female's preferred and usual lifestyle.

4.4. Sponsor Qualified Medical Personnel

The contact information for the sponsor's appropriately qualified medical personnel for the trial is documented in the study contact list located in the coordinator's manual/team SharePoint site/study portal.

To facilitate access to appropriately qualified medical personnel on study related medical questions or problems, subjects are provided with a contact card. The contact card contains, at a minimum, protocol and investigational compound identifiers, subject study number, contact information for the investigational site, and contact details for a help desk in the event that the investigational site staff cannot be reached to provide advice on a medical question or problem originating from another healthcare professional not involved in the subjects participation in the study. The help desk number can also be used by investigational staff if they are seeking advice on medical questions or problems, however it should only be used in the event that the established communication pathways between the investigational site and the study team are not available. It is therefore intended to augment, but not replace the established communication pathways between the investigational site and study team for advice on medical questions or problems that may arise during the study. The help desk number is not intended for use by the subject directly and if a subject calls that number they will be directed back to the investigational site.

5. STUDY TREATMENTS

Study treatment groups will be oral sildenafil 5 mg TID, sildenafil 20 mg TID, and sildenafil 80 mg TID; study treatment assignments will be blinded. Blinded sildenafil treatment is to continue for the duration of the subject's participation in the study. Subjects who discontinue from the assigned study treatment will continue to be followed for the primary endpoint of mortality.

No prior long term treatment with PDE-5 inhibitors or treatment with bosentan or riociguat will be permitted at study entry. Background treatment with endothelin receptor antagonists (ETRA) other than bosentan (ie, ambrisentan and any other ETRA that becomes available during the conduct of the study provided that the new agent is not a potent CYP3A inducer or inhibitor (Appendix 1) and does not have any clinically evident drug-drug interaction with sildenafil) and/or prostanoids will be allowed and is to be continued during the study. Add-on treatment specific for PAH with drug classes other than PDE-5 inhibitors (ie, ETAs as described above, oral, inhaled or subcutaneous (SC) prostanoids, or IV epoprostenol) will be permitted as needed for clinical worsening during the trial. Any other novel agents that are approved for use in adult PAH that become available during the course of the study will be permitted as long as they don't have any clinically evident drug-drug interactions and are in the opinion of the investigator safe when co-administered with sildenafil. Subjects who receive treatment with bosentan or riociguat will be discontinued from study treatment, but followed for survival through the end of the study. While add-on treatment in accord with subject need is allowed, it will be discouraged until after the assessment of 6MWD at Month 12 provided that this is consistent with the best interest of the subject. Supportive non-PAH-specific treatment (eg, oxygen, digoxin, diuretics and inotropes) will be permitted at any time during the study.

5.1. Allocation to Treatment Randomization

Subjects will be randomly assigned on a 1:1:1 basis to either blinded sildenafil 5 mg (TID), 20 mg (TID) or 80 mg (TID) at the Baseline visit (Day 1) after successfully fulfilling all inclusion and exclusion criteria.

Table 1. Allocation to Treatment

Treatment Group	Number of Subjects Randomly Assigned
Sildenafil 5 mg TID	143
Sildenafil 20 mg TID	143
Sildenafil 80 mg TID	143

Treatment with blinded study treatment will begin with the 1st dose being administered at the clinic on Day 1.

A central randomization scheme using an automated interactive voice response system (IVRS/IWRS) incorporating a central randomization and drug supply scheme will be used. Instructions on IVRS/IWRS will be provided under separate cover.

5.2. Breaking the Blind

The study will be sponsor, subject and investigator blinded. At the initiation of the study, the study site will be instructed on the method for breaking the blind. The method will be either a manual or electronic process. Blinding codes should only be broken in emergency situations for reasons of subject safety. Whenever possible, the investigator or sub-investigator consults with a member of the study team prior to breaking the blind. When the blinding code is broken, the reason must be fully documented and entered on the case report form. The subject will be discontinued from study treatment, but will continue to be followed for survival at the timepoints specified in the schedule of activities for the duration of the study.

5.3. Drug Supplies

5.3.1. Formulation and Packaging

The study medication will be provided as blinded tablets of 5 mg, 20 mg, and 80 mg sildenafil and corresponding matching placebo. All study medication will be dispensed in double-blind, triple-dummy blisters in cartons.

Formulation and Packaging			
Treatment Group	Active Treatment	Placebo Tablet	Placebo Tablet
Sildenafil 5 mg TID	5 mg tablets	20 mg matching placebo	80 mg matching placebo
Sildenafil 20 mg TID	20 mg tablets	5 mg matching placebo	80 mg matching placebo
Sildenafil 80 mg* TID	80 mg tablets	5 mg matching placebo	20 mg matching placebo

*** Subjects randomly assigned to 80 mg dose will receive 20 mg TID starting on Day 1 for 2 weeks and then be titrated up to their randomized dose. Subjects randomly assigned to the 5 and 20 mg doses will start on their randomized dose on Day 1.**

The investigator or designee (eg, pharmacist), will ensure that all study drug is stored in a secured area, under recommended storage conditions and in accordance with applicable regulatory requirements. Study staff (study coordinator, research nurse or pharmacist, as designated in site study delegation log) will dispense test article to the subject.

5.3.2. Preparation and Dispensing

Subjects will be provided with tablets of the strength 5 mg or 20 mg or 80 mg and corresponding matching placebo for the other 2 strengths. Three tablets (1 active plus 2 placebos) will be taken orally three times per day. The medication will be provided in blisters in cartons. Each 3 tablet dose will be identified by time (morning, afternoon, evening) and segregated by day. Subjects randomly assigned to 80 mg TID must start on 20 mg TID and be titrated up to 80 mg TID at Week 2. These subjects will be dispensed blinded 20 mg tablets and placebo (for 5 mg and 80 mg doses) for 2 weeks. At the Week 2 visit, the randomized dose of 80 mg TID will be dispensed to these subjects (with 5 mg and 20 mg placebo). Subjects randomly assigned to the 5 mg and 20 mg TID dose groups will be dispensed their assigned treatment on Day 1. To maintain the blind, all subjects will be provided with a 2- week supply of study medication on Day 1 and then will return to the clinic for a Week 2 visit. The first dose of study medication will be administered at the study site. Blinded study drug will be provided in blister packs. At all visits subjects will be provided with sufficient number of blister packs to ensure supplies last to their next visit.

5.3.3. Administration

On Day 1, subjects will be randomly assigned to one of the three blinded groups: 5 mg sildenafil, 20 mg sildenafil or 80 mg sildenafil (TID) in a 1:1:1 ratio. Subjects randomly assigned to 80 mg dose will receive 20 mg TID on Day 1 and for 2 additional weeks, and then titrated up to their randomized dose of 80 mg TID at Week 2. Subjects randomly assigned to the 5 and 20 mg doses will start their randomized dose on Day 1.

At Baseline (Day 1), the subject will be given their morning dose in the clinic. The subject will be instructed to take three tablets three times a day at least 4-6 hours apart with or without food. Instruction on storage requirements will be provided to the subject at this time.

If a subject misses a dose, he/she should take it as soon as it is remembered, but no later than 4 hours before the next dose.

For study visits in which the 6MWT will be performed (Months 6, 12, 18, 24, 30,36, 42, 48 and every 6 months thereafter as well as end-of-treatment visit) subjects will be instructed to take their morning dose approximately 4 to 6 hours prior to the scheduled 6MWT time.

Subjects who temporarily discontinue study treatment (for up to 14 days) due to required short-term treatment of prohibited medications, such as nitrates, can be restarted on study treatment. Sublingual nitroglycerin can be used in an acute situation but the subject will need to discontinue study treatment if frequent/chronic use is required.

In the event that subject is unable to tolerate the study medication, they will be withdrawn from the study treatment, but will continue to be followed for survival at the timepoints specified in the schedule of activities for the duration of the study. All reasons for study drug withdrawal will be documented in the CRF.

Subject will be asked to return cartons (containing used and unused blister packs) at each visit and will be issued enough supplies for treatment until the next visit.

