5.5. Concomitant Medication(s)

Concomitant medications should remain stable throughout the treatment phase of the study, where possible. Changes in concomitant medications can and should be made where issues of subject safety are evident. Current country label or Investigator’s Brochure should be consulted to determine other medications that cannot be administered with sildenafil citrate.

Prohibited During Study

- Bosentan is not permitted. Subjects who receive bosentan will be discontinued from study treatment and followed for survival for the duration of the study;
- Riociguat is not permitted. Subjects who receive riociguat will be discontinued from study treatment and followed for survival for the duration of the study;

- Any agent that is a potent CYP3A inducer or inhibitor (Appendix 1) that has the potential for any clinically evident drug-drug interaction with sildenafil;
- Concomitant therapy with any PDE-5 inhibitor; and
- Nitrates or nitric oxide. Sildenafil was shown to potentiate the hypotensive effects of nitrates, and its administration to patients who are using organic nitrates, either regularly and/or intermittently, in any form is contraindicated.

Permitted During Study

- Background treatment with endothelin receptor antagonists (ETRA) other than bosentan (ie, ambrisentan and any other ETRA that becomes available during the conduct of the study provided that the new agent is not a potent CYP3A inducer or inhibitor that has any clinically evident drug-drug interaction with sildenafil) and/or prostanoids will be permitted and is to be continued during the study.
- Add-on treatment specific for PAH with drug classes other than PDE-5 inhibitors (ie, ETAs as described above, oral, inhaled or SC prostanoids, or IV epoprostenol) will be permitted as needed for clinical worsening during the trial.
- Any other novel agents that are approved for use in adult PAH that become available during the course of the study will be permitted as long as there are no clinically evident drug-drug interactions and are in the opinion of the investigator safe when co-administered with sildenafil.
- Supportive non-PAH-specific treatment (eg, oxygen, digoxin, diuretics and inotropes) will be permitted at any time during the study.
- Warfarin (and other vitamin K antagonists), angiotensin-converting enzyme (ACE) inhibitors, angiotensin-2 receptor blockers (ARB), calcium channel blockers will be permitted during the study.

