6.10. Subject Withdrawal

Subjects may withdraw from the study at any time at their own request, or they may be withdrawn at any time at the discretion of the investigator or sponsor for addition of prohibited medication, safety or behavioral reasons, or the inability of the subject to comply with the protocol required schedule of study visits or procedures at a given study site.

If a subject does not return for a scheduled visit, every effort should be made to contact the subject. All attempts to contact the subject and information received during contact attempts must be documented in the subject's medical record. In any circumstance, every effort should be made to document subject outcome, if at all possible. The investigator should inquire about the reason for withdrawal, request the subject to return all unused investigational product(s), request the subject to return for a final visit, if applicable, and follow up with the subject regarding any unresolved adverse events (AEs).

If the subject withdraws from the study, and also withdraws consent for disclosure of future information, no further evaluations should be performed, and no additional data should be collected. The sponsor may retain and continue to use any data collected before such withdrawal of consent.

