17. APPENDICES

Appendix 1. CYP3A Inhibitors or Inducers

The FDA classification of CYP enzyme inhibitors and inducers are provided in the tables below. For the purposes of this protocol, both strong and moderate inhibitors of the CYP3A enzyme (≥ 2 -fold increase in AUC or $>50\%$ decrease in clearance of a substrate) are considered to be potent inhibitors and are therefore prohibited during the study. Similarly, both strong and moderate inducers of the CYP3A enzyme ($>50\%$ decrease in AUC of a substrate) are prohibited during the study.

Please refer to the shaded areas of the tables below for prohibited drugs. These lists are not exhaustive. Other drugs known or expected to result in a similar effect on CYP3A enzymes should also be avoided.

Classification of In Vivo Inhibitors of CYP Enzymes⁽¹⁾

CYP Enzymes	Strong Inhibitors ⁽²⁾ ≥ 5 -fold increase in AUC or $> 80\%$ decrease in CL	Moderate inhibitors ⁽³⁾ ≥ 2 but < 5 -fold increase in AUC or 50-80% decrease in CL	Weak inhibitors ⁽⁴⁾ ≥ 1.25 but < 2 -fold increase in AUC or 20-50% decrease in CL
CYP1A2	ciprofloxacin, enoxacin, fluvoxamine	methoxsalen, mexiletine, oral contraceptives, phenylpropanolamine, thiabendazole, vemurafenib, zileuton	acyclovir, allopurinol, caffeine, cimetidine, daidzein, ⁽⁵⁾ disulfiram, echinacea, ⁽⁵⁾ famotidine, norfloxacin, propafenone, propranolol, terbinafine, ticlopidine, verapamil
CYP2B6			clopidogrel, ticlopidine, prasugrel
CYP2C8		gemfibrozil ⁽⁶⁾	fluvoxamine, ketoconazole, trimethoprim
CYP2C9		amiodarone, fluconazole, miconazole, oxandrolone	capecitabine, cotrimoxazole, etravirine, fluvastatin, fluvoxamine, metronidazole, sulfapyrazone, tigecycline, voriconazole, zafirlukast
CYP2C19	fluconazole, ⁽⁷⁾ fluvoxamine, ⁽⁸⁾ ticlopidine ⁽⁹⁾	esomeprazole, fluoxetine, moclobemide, omeprazole, voriconazole	allicin (garlic derivative), armodafinil, carbamazepine, cimetidine, etravirine, human growth hormone (rhGH), felbamate, ketoconazole, oral contraceptives ⁽¹⁰⁾

CYP Enzymes	Strong Inhibitors⁽²⁾ ≥ 5-fold increase in AUC or > 80% decrease in CL	Moderate inhibitors⁽³⁾ ≥ 2 but < 5-fold increase in AUC or 50-80% decrease in CL	Weak inhibitors⁽⁴⁾ ≥ 1.25 but < 2-fold increase in AUC or 20-50% decrease in CL

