Appendix 2. Six-Minute Walk Test Protocol

The following protocol **MUST** be used to administer the 6-minute walk test. This is in compliance with the ATS statement: Guidelines for the six-minute walk test.

Please note that nitrates (in any form) may not be administered at any time during the course of this study.

A separate checklist/worksheet will be provided by Pfizer prior to study initiation and it is important that this checklist is completed prior to each 6-minute walk test being performed. This will help improve standardization and reduce variability across sites.

In accordance with the ATS Guidelines for the 6-minute walk, all technicians must be trained in performing the 6-minute walk and evidence that this training has been completed needs to be documented (for example in the site initiation visit report) by the Pfizer Study Personnel prior to study initiation. Ideally, the same tester should perform all the tests for all subjects at each site. If this is not possible, the same tester should ideally perform all tests for a particular subject.

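### Protocol 5.3.3 provides for nitrate use that Appendix 2 bars outright, and does not say whether study drug stops during acute use, so its fit with the section 5.5 contraindication is unclear

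*Protocol*

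**What the plan says.** Three places in the protocol address nitrates during treatment.

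- **Section 5.3.3 (Administration)** has two consecutive sentences. The first says that subjects who stop study treatment temporarily, for up to 14 days, "due to required short-term treatment of prohibited medications, such as nitrates, can be restarted on study treatment". The second says: "Sublingual nitroglycerin can be used in an acute situation but the subject will need to discontinue study treatment if frequent/chronic use is required".
- **Section 5.5 (Concomitant Medications)** lists nitrates and nitric oxide under the drugs prohibited during the study. It notes that sildenafil potentiates the hypotensive effect of nitrates and says of sildenafil that "its administration to patients who are using organic nitrates, either regularly and/or intermittently, in any form is contraindicated".
- **Appendix 2 (Six-Minute Walk Test Protocol)** says: "Please note that nitrates (in any form) may not be administered at any time during the course of this study".

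Neither section 5.5 nor Appendix 2 makes an exception for acute use or refers to 5.3.3, and 5.3.3 refers to neither of them. Exclusion criterion 12 covers current nitrate treatment at entry and does not address use after randomization.

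SAP 5.6 names receipt of an excluded concomitant medication as a possible significant protocol deviation. It leaves the list of such medications, and the deviations that exclude subjects from the per-protocol analyses, to be specified before database lock.

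**The concern.** The hazard is one that the protocol names itself: a fall in blood pressure when sildenafil and a nitrate are combined. In an acute situation, a site that opens 5.3.3 finds a permission, and a site that opens Appendix 2 or section 5.5 finds a ban. A site that acts on 5.3.3 breaches the words of Appendix 2, and nothing in the protocol says which text governs.

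There is also a smaller analytical consequence. The per-protocol time-to-event analysis in SAP 5.2 counts events that occur on study treatment without major deviations, up to 35 days after the last dose. Whether nitroglycerin taken under 5.3.3 is an excluded medication therefore bears on which events that analysis counts, and the protocol supplies no single rule for deciding it.

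**Working it through.** There is no figure to reproduce; the check is a comparison of the texts.

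**Step 1. What 5.3.3 settles.** It permits acute sublingual nitroglycerin and requires study treatment to be discontinued if use becomes frequent or chronic. It does not say what happens to study drug during acute use. Two readings are open:

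- *Reading A:* study drug continues. This is the natural implication of attaching discontinuation only to repeated use.
- *Reading B:* study drug is interrupted and restarted. The preceding 14-day sentence, which names nitrates as an example, can be taken to cover acute use.

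**Step 2. Each use against each prohibition.**

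| Use under 5.3.3 | Appendix 2: no nitrate of any form during the study | Section 5.5: sildenafil contraindicated with regular or intermittent nitrate use |
|---|---|---|
| Acute nitroglycerin, reading A (study drug continues) | Contradiction | Contradiction |
| Acute nitroglycerin, reading B (study drug interrupted) | Contradiction | No contradiction |
| Short nitrate course with study drug stopped for up to 14 days | Contradiction | No contradiction |

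The Appendix 2 column does not depend on the reading, because that sentence concerns giving the nitrate, whatever happens to sildenafil. The section 5.5 column does depend on it, because the contraindication concerns giving sildenafil to someone who is using nitrates.

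**Step 3. The prohibited heading in 5.5.** Listing nitrates as prohibited sits awkwardly with 5.3.3 on any reading. However, 5.3.3 itself calls nitrates prohibited and then says how their use is handled, so the heading alone is weak evidence of conflict.

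**Step 4. Reach into the analysis.** SAP 5.1 defines the intent-to-treat population as randomized and treated subjects. Protocol 9.2.1 counts all deaths to the end of the trial, including those after discontinuation. Classifying nitrate use as a deviation or not changes neither rule. The per-protocol analyses do depend on that classification, and SAP 5.2 makes them sensitivity analyses.

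**The case against.** The best defence is that 5.3.3 is a specific provision qualifying a general list. It acknowledges that nitrates are prohibited, provides for interruption and restart, and requires discontinuation if use is repeated. Read that way, it manages a breach of 5.5 and does not license one. Section 5.5 also opens by allowing changes in concomitant medication for subject safety.

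Part of this stands. A reader might infer that 5.3.3 authorizes nitroglycerin while study drug continues. The documents do not say so: that is an implication of the wording, and the preceding sentence supports the other reading. The contradiction with the 5.5 contraindication is therefore conditional.

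A reader might also infer that the protocol states no consequence for nitrate use, since 5.5 gives one for bosentan ("Subjects who receive bosentan will be discontinued from study treatment and followed for survival for the duration of the study") and none for nitrates. That is not supported either, because 5.3.3 supplies consequences. What is missing from 5.5 is a pointer to them.

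The defence does not remove the conflict with Appendix 2. That appendix concerns the walk test, which might suggest a narrower purpose, but its sentence is expressly study-wide. The safety clause at the start of 5.5 does not expressly lift the nitrate bar. Nor does the protocol anywhere say that 5.3.3 prevails.

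**Conclusion.** The inconsistency is real and worth correcting. Section 5.3.3 and Appendix 2 cannot both be followed, on either reading of 5.3.3. Section 5.3.3 also contradicts the contraindication in 5.5 if study drug continues during acute use, and the protocol leaves that point unclear. The first conclusion rests only on the stated words; the second rests on reading A, which is plausible but not expressed.

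The stakes are subject safety, site conduct and the per-protocol sensitivity analyses. The number of subjects who received a nitrate is not in the documents, so no shift in any estimate is claimed. A reader might infer that the primary mortality result is compromised; nothing in the documents supports this, because the intent-to-treat rules do not depend on how nitrate use is classified.

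**What to change.** Reconcile 5.3.3, 5.5 and Appendix 2 into one nitrate rule. The sponsor's clinicians choose the rule; this review takes no view on which is right. The text should say explicitly whether study drug is interrupted with acute use, and 5.5 and Appendix 2 should refer to the section that states it.

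Then, if the database is not yet locked, classify two cases consistently with that rule in the excluded-medication list under SAP 5.6: acute nitroglycerin, and a short nitrate course with study drug interrupted. The documents give no lock date; SAP version 2 is dated 24 March 2021. If lock has passed, the clinical study report should say how these cases were handled.

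The cost is wording in three places and two entries in a list that is already planned. Sample size, alpha and the primary analysis do not change. Reach is limited for site conduct: Appendix 6 reports that sites were told to hold End of Treatment visits by 15 August 2020, apart from subjects without post-study treatment options, so a corrected instruction reaches only those kept on treatment under that appendix, whose title names five countries. Before lock, the classification could still cover all subjects, because section 5.5 requires every concomitant medication to be entered on the CRF.
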